4.2. Scientific Rationale for Study Design

The purpose of the study is to evaluate the safety and tolerability of duvelisib in combination with pembrolizumab in subjects with R/M HNSCC and determine if the addition of duvelisib to pembrolizumab may improve treatment responses.

Pembrolizumab was selected for combination with duvelisib in this study for the following reasons:

1. Strong antitumor synergy (i.e., inhibition of tumor growth and increase in survival) was observed for the combination of duvelisib and a PD-1 inhibitor vs either monotherapy *in vivo* ([Pachter 2018](#), [Davis 2017](#))
2. Pembrolizumab (Keytruda[®]) is approved for R/M HNSCC ([Keytruda 2019](#))

As this is the first clinical study of duvelisib in subjects with R/M HNSCC, the first 6 subjects in Stage 1 will be evaluated for DLTs. Furthermore, a 1-week duvelisib monotherapy lead-in has been included so that subjects can be monitored on monotherapy and a steady-state duvelisib PK sample and biomarker samples can be obtained before the treatment with pembrolizumab is started. The lead-in design with duvelisib is expected to provide scientific and safety information for the potential contribution of duvelisib in this combination setting.

The efficacy endpoints will be assessed using the standard RECIST v 1.1 ([Eisenhauer 2009](#)), which were also used in the registrational study for pembrolizumab in HNSCC ([Keytruda 2019](#)). Justification for Dose of Study Interventions

The combination of the 25 mg BID dosage of duvelisib and the 200 mg q3w dosage of pembrolizumab was selected based on the approved dosage for duvelisib in patients with hematologic malignancies ([COPIKTRA 2018](#)) and the approved dosage for pembrolizumab in patients with R/M HNSCC ([Keytruda 2019](#)).

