Serum or Urine hCG Pregnancy Test for Women of	X	X ^e			X	X		X		A serum pregnancy test must be performed within 7 days of first duvelisib dose. At subsequent time points, serum testing is preferred but urine testing is allowed if a

		Duvelisib Lead-in	Duvelisib in Combination with Pembrolizumab ^a				End of Treatment and Follow-up			
Activity ^b	Screening (D-30 to D -1)	Cycle 1 (4 weeks)			Cycle 2 and Cycle 3 (3 weeks)	Cycles ≥ 4 (3 weeks)	EoT ^c	Safety F/U 30 D (+7) postdose) ^d	Survival F/U Every 3 months until End of Study	Notes
		W1	W2	W3	W1	W1				
		D1	D8 ± 5	D15 ± 3	D1 ± 3	D1 ± 3				
Childbearing Potential										blood draw for other assessments is not performed. A positive urine test result must be confirmed by a serum test. See Table 23 .
Clinical Chemistry with Liver Function Tests	X	X	X	X	X	X	X	X		BUN, potassium, creatinine, sodium, total protein, glucose (fasting), calcium, LDH, ALT, AST, total and direct bilirubin, and ALP. Screening test results can be used for C1D1 if tests are performed within 7 days of first dose. See Table 23 .
Hematology	X	X	X	X	X	X	X	X		Hematology panel plus a 5-part differential. Screening test results can be used for C1D1 if tests are performed within 7 days of first dose. See Table 23 .
Urinalysis	X		X		X	X		X		See Table 23 .
Imaging and Disease Response Assessment via RECIST v 1.1 (Eisenhauer 2009)	X					X	X ^f			See Section 8.1. After Screening disease assessment, response will be assessed at C4D1 (10 weeks after first dose of duvelisib) and then D1 of every third cycle thereafter (approximately every 9 weeks). The same method of assessment used at Screening should be used throughout the study. In the case of a CR or PR, a confirmatory scan must be performed per RECIST v 1.1. It is recommended that this scan be performed at 4 (+1) weeks after the initial response.
FDA-approved PD-L1 Testing (if required)	X									Perform if specified in the current pembrolizumab prescribing information (Keytruda 2019), if results are not already available. Information on FDA-approved tests is available at: http://www.fda.gov/CompanionDiagnostics .

		Duvelisib Lead-in	Duvelisib in Combination with Pembrolizumab ^a				End of Treatment and Follow-up			
Activity ^b	Screening (D-30 to D -1)	Cycle 1 (4 weeks)			Cycle 2 and Cycle 3 (3 weeks)	Cycles ≥ 4 (3 weeks)	EoT ^c	Safety F/U 30 D (+7) postdose) ^d	Survival F/U Every 3 months until End of Study	Notes
		W1	W2	W3	W1	W1				
		D1	D8 ± 5	D15 ± 3	D1 ± 3	D1 ± 3				

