^g Blood for biomarker assessments and tumor biopsy may be obtained either at Screening or at first dose of duvelisib on C1D1 (preferred).

^h Please refer to [Table 2](#) for assessments and timing for C4D1 and beyond.

ⁱ Every effort will be made to administer the first dose of pembrolizumab on Day 8 of Cycle 1 (C1D8). If the first dose of pembrolizumab on C1D8 is delayed, every effort should be made to delay the subsequent dosing of the next cycle (within the protocol-allowed window of 3 days) to achieve as close to a 3-week interval between pembrolizumab doses as possible. The Medical Monitor needs to be consulted for such adjustments to ensure uniformity of approach and to account for subject-specific circumstances. For example, if the third day of the C2D1 window falls on a weekend, an additional adjustment would need to be

Protocol VS-0145-130, Version 2.0
Duvelisib

Verastem, Inc.

made on a case-by-case basis. In the event of a delay of the start of pembrolizumab therapy, DLTs will be evaluated at the end of the third week of combination therapy.

Table 2: Pharmacokinetic, Pharmacodynamic, and Biomarker Sampling in Stage 1

Cycle	Day	Sampling Time Points ^a	PK Samples	Whole Blood for PDn Analysis	Serum and Plasma for Biomarkers	Whole Blood for Immune Cell Analysis	Stool Sample for Biomarker Analysis ^b	Swab for Genomic Analysis	Tumor Biopsies ^c
Screening or C1D1					X ^d	X ^d	X ^e	X ^d	X ^{d, f}
1	8	Pre-duvelisib dose ^g	X ^g	X	X	X			
1	8	1 hour (\pm 10 min) after duvelisib dose	X ^g	X					
1	8	2 hours (\pm 10 min) after duvelisib dose	X ^g						
1	8	Approximately 2 to 4 hours after duvelisib dose	X ^g						X ^{f, g}
1	8	0 hours (\pm 5 min) after the end of pembrolizumab infusion	X						
1	15	Predose	X						
2	1	Predose ^h	X	X	X	X			
2	1	0 hours (\pm 5 min) after the end of pembrolizumab infusion	X						
2	1	1 hour (\pm 10 min) after the end of pembrolizumab infusion	X						
2	1	2 hours (\pm 10 min) after the end of pembrolizumab infusion	X						
3	1	Predose ⁱ	X						
4	1	Predose ⁱ	X		X	X	X ^j		
5	1	Predose ⁱ	X						

Protocol VS-0145-130, Version 2.0
Duvelisib

Verastem, Inc.

Cycle	Day	Sampling Time Points ^a	PK Samples	Whole Blood for PDn Analysis	Serum and Plasma for Biomarkers	Whole Blood for Immune Cell Analysis	Stool Sample for Biomarker Analysis ^b	Swab for Genomic Analysis	Tumor Biopsies ^c
≥ 7 ^k	1	Predose ⁱ			X	X			
End of treatment					X	X			

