^h Predose sample is to be taken before either study intervention (i.e., duvelisib or pembrolizumab) is administered. On C2D1, duvelisib will be administered 30 minutes before the start of the pembrolizumab infusion

ⁱ Predose sample is to be taken before either study intervention (i.e., duvelisib or pembrolizumab) is administered. The pembrolizumab infusion should be started within 10 minutes after the dose of duvelisib is administered.

^j The C4D1 stool sample may be collected up to 3 days before C4D1.

^k Samples will be collected on C7D1 and D1 of every third cycle thereafter (approximately every 9 weeks) or until the Sponsor terminates the collection.

1.4. Schedule of Activities (SoA) for Stage 2

Table 3: Study Activities for Stage 2: Duvelisib in Combination with Pembrolizumab

		Duvelisib in Combination with Pembrolizumab ^a			End of Treatment and Follow-up			
Activity ^b	Screening (D-30 to D -1)	Cycle 1 (3 weeks)	Cycle 2 and Cycle 3 (3 weeks)	Cycles ≥ 4 (3 weeks)	EoT ^c	Safety F/U 30 D (+7) postdose) ^d	Survival F/U Every 3 months until End of Study	Notes
		W1	W1	W1				
		D1±3	D1 ±3	D1 ±3				
Informed Consent	X							Potentially eligible subjects must sign an ICF before initiating any study specific procedures. SOC assessments that fulfill study eligibility requirements may be performed before the subjects signs the ICF.
Inclusion/Exclusion Criteria	X							Reconfirm eligibility before first dose.
Medical and Disease History, Demographics	X							Medical and Disease History includes histologic or cytologic diagnosis of HNSCC; HPV status; prior PD-L1 expression; and prior treatment information.
Archival Tumor Tissue	X							Archived tumor tissue should be submitted from all enrolled subjects, if available.
Physical Examination	X	X	X	X	X			See Section 8.2.1. Full examination (including height) at Screening and symptom-directed at subsequent time points. Screening results can be used for C1D1 if assessments are performed within 7 days of first dose.
Vital Signs and Weight	X	X	X	X	X	X		See Section 8.2.1. Vital signs measured with subject in a semi-supine position after 5 minutes rest. Includes temperature, systolic and diastolic blood pressure, pulse rate, and respiratory rate.
ECOG Performance Status	X	X	X	X	X	X		See Section 8.3.1. Screening ECOG results can be used for C1D1 if test is performed within 7 days of first dose.

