2.4.1. Risk Assessment

As the effect of duvelisib in subjects with R/M HNSCC is unknown, Stage 1 of the study includes a 1-week lead-in with duvelisib monotherapy to monitor for safety and biomarker sampling before the initiation of combination therapy with duvelisib and pembrolizumab.

For subjects with hematologic malignancies, clinical study results to date support a favorable benefit-risk assessment of duvelisib. The risks of duvelisib for subjects with hematologic malignancies are consistent with the adverse event (AE) profile for the PI3K inhibitor drug class and AEs experienced by patients undergoing treatment for advanced cancers. Important identified risks of duvelisib include infections, diarrhea/colitis, cutaneous reactions, pneumonitis, neutropenia, and alanine aminotransferase (ALT)/aspartate aminotransferase (AST) elevation. Potential risks include hepatotoxicity, drug-drug interaction (DDI), and reproductive toxicity. These toxicities are managed using a combination of prophylaxis, supportive care, and dose modifications. Guidance on management of these AEs, including duvelisib dose interruptions and modifications, is provided in Section 6.6 and Section 6.7. Detailed information about the known and expected risks and reasonably expected AEs of duvelisib may be found in the Investigator's Brochure (IB).

The identified risks of pembrolizumab ([Keytruda 2019](#)) are infusion reactions and the following immune-mediated conditions: pneumonitis, colitis, hepatitis, endocrinopathies, nephritis and renal dysfunction, and cutaneous adverse reactions (including rash). Refer to the pembrolizumab prescribing information for guidance on management of these AEs ([Keytruda 2019](#)).

Based on the monotherapy safety profiles for each drug, potential overlapping toxicities for duvelisib in combination with pembrolizumab include non-infectious diarrhea or colitis, cutaneous reactions, pneumonitis without suspected infectious cause, and elevations in ALT and AST levels (Section 6.6.1). These events will be closely monitored during the study.

Although duvelisib has not yet been evaluated in subjects with solid tumors, initial safety results for an ongoing first-in-human study of the oral selective inhibitor of PI3K- γ (IPI-549) in combination with nivolumab in patients with melanoma, non-small cell lung cancer (NSCLC), or HNSCC demonstrated favorable tolerability ([Sullivan 2018](#)).

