Evaluate potential biomarkers for possible associations with clinical efficacy and/or safety outcomes of duvelisib in combination with pembrolizumab	
• Blood assessments of immune cell populations, chemokines, cytokines and circulating tumor DNA• Fecal assessments of protein, DNA, and/or RNA• Tumor biopsy evaluation of biomarkers such as gene and copy number variation, RNA expression, protein expression, and/or immune cell content (Required biopsies in Stage 1 and optional biopsy in Stage 2)• ORR and its relationship to tumor and/or immune cell programmed cell death ligand 1 (PD-L1) levels and to tumor human papillomavirus (HPV) status

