4. STUDY DESIGN

4.1. Overall Design

This is a multicenter, non-randomized, open-label, Phase 1b/2 study of duvelisib in combination with pembrolizumab in subjects with R/M HNSCC who are eligible for pembrolizumab monotherapy based on the current pembrolizumab prescribing information ([Keytruda 2019](#)). This study will be conducted at multiple sites in the US and will include approximately 13 subjects in Stage 1 and 17 additional subjects in Stage 2, for a total of 30 subjects in the final analysis.

The study will follow a Simon two-stage design ([Simon 1989](#)).

The study stages are depicted in [Figure 1](#) and the treatment/imaging schemes for Stage 1 and Stage 2 are depicted in [Figure 2](#) and [Figure 3](#), respectively.

Subjects will receive duvelisib 25 mg BID orally (PO) in combination with pembrolizumab 200 mg every 3 weeks (q3w) intravenously (IV).

In **Stage 1**, subjects will have a 1-week lead-in with duvelisib before the initiation of combination therapy with duvelisib and pembrolizumab. Approximately 13 subjects are planned to be accrued in this stage. The first 6 subjects will be assessed for dose-limiting toxicities (DLTs). The DLT evaluation period will be Cycle 1 (4 weeks or 28 days): the 1-week duvelisib monotherapy lead-in period followed by 1 dose of pembrolizumab in combination with 3 additional weeks of continuous dosing of duvelisib. Every effort will be made to administer the first dose of pembrolizumab on Day 8 of Cycle 1 (C1D8). If the first dose of pembrolizumab on C1D8 is delayed, every effort should be made to delay the subsequent dosing of the next cycle (within the protocol-allowed window of 3 days) to achieve as close to a 3-week interval between pembrolizumab doses as possible. The Medical Monitor needs to be consulted for such adjustments to ensure uniformity of approach and to account for subject-specific circumstances. For example, if the third day of the C2D1 window falls on a weekend, an additional adjustment would need to be made on a case-by-case basis. In the event of a delay of the start of pembrolizumab therapy, DLTs will be evaluated at the end of the third week of combination therapy.

The DLT evaluation period will be used to assess DLTs in the first 6 subjects.

- If there is ≤ 1 DLT in the 6 DLT-evaluable subjects, additional subjects will be enrolled to bring the total dosed in Stage 1 to approximately 13 subjects.

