- If there are ≥ 2 DLTs in the first 6 subjects, enrollment at duvelisib 25 mg BID will stop. Enrollment would restart at a reduced duvelisib dose (15 mg BID) to assess DLTs at the lower dose (dose level -1; see [Table 6](#)).

Table 6: Duvelisib Dose Levels

Dose Level	Duvelisib, mg BID PO
Starting Dose	25
-1	15

Abbreviations: BID: twice daily; PO: oral.

A formal analysis of available safety data will be conducted when the first 10 subjects treated have received at least 1 cycle of study treatment. This will enable assessment of toxicities of later onset, particularly outside of the DLT window.

If an excessive rate of Grade 3 or higher overlapping SAEs (defined as any rate for each SAE that is above the highest reported in warnings and precautions of the prescribing information for either duvelisib [COPIKTRA 2018] or pembrolizumab [Keytruda 2019], respectively), such as pneumonitis, colitis, cutaneous skin reactions, and elevations of AST/ALT, is observed outside of the DLT window, a decision for stopping or modifying the study may be made. However, recognizing that the observed rate of such events can be highly sensitive due to the small sample size, the totality of safety data will be reviewed and carefully considered prior to making a formal decision.

An interim analysis of ORR will occur after all of the planned 13 subjects in Stage 1 are enrolled, dosed, and have been followed through at least the first disease response assessment.

- If there are \leq 2 responses (CR or PR) in the 13 subjects in Stage 1, further accrual in the study may be stopped. However, all available data, including the relative proportion of CRs, will be analyzed before a final decision is made.
- If > 2 responses are observed in Stage 1, enrollment will continue in Stage 2.

In **Stage 2**, 17 additional subjects will be accrued for a total of 30 subjects in the final analysis. Subjects enrolled in Stage 2 will only receive combination therapy with duvelisib and pembrolizumab. Enrollment into Stage 2 may proceed prior to completion of the interim analysis as long as at least 2 of the 13 subjects enrolled in Stage 1 have a confirmed response.

The ORR and PFS will be assessed according to Response Evaluation Criteria in Solid Tumors (RECIST) v 1.1 (Eisenhauer 2009).

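### Table 1's D8 ± 5 window lets the stated 1-week duvelisib lead-in shrink to 2 days; an early limit of Day 7 would protect it at almost no cost.

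*Combined protocol and SAP*

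**What the plan says.** Section 2.4.1 gives the reason for the lead-in: "Stage 1 of the study includes a 1-week lead-in with duvelisib monotherapy to monitor for safety and biomarker sampling", before combination therapy begins. Section 4.2 repeats it ("a 1-week duvelisib monotherapy lead-in has been included so that subjects can be monitored on monotherapy") and adds a steady-state duvelisib PK sample and biomarker samples ahead of pembrolizumab. Sections 4.1 and 6.7 build the 28-day DLT period from this week plus three weeks of combination.

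The target day is set in Section 4.1: "Every effort will be made to administer the first dose of pembrolizumab on Day 8 of Cycle 1 (C1D8". Table 1 (Section 1.3) heads that visit D8 ± 5 and the following one D15 ± 3. Footnote a exempts Cycle 1 from counting days from the pembrolizumab dose, so both visits count from the first duvelisib dose. The row "Clinical Chemistry with Liver Function Tests" is marked at D1, D8, D15 and C2D1.

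The special rules cover lateness only. Footnote i says: "If the first dose of pembrolizumab on C1D8 is delayed, every effort should be made to delay the subsequent dosing of the next cycle". Sections 4.1 and 6.7 repeat this, require the Medical Monitor to be consulted on such adjustments, and move the DLT evaluation to the end of the third combination week. Nothing is said about an early dose.

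Stage 2 has no lead-in: "Subjects enrolled in Stage 2 will only receive combination therapy with duvelisib and pembrolizumab".

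**The concern.** The lead-in exists to observe subjects on duvelisib alone and to sample them on duvelisib alone. The visit that ends it has the widest on-treatment window in Table 1; the other windowed on-treatment visits are ± 3. A site that doses on Day 3 is within schedule but has given about two days of monotherapy instead of a week.

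Three things depend on that week:

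- **Safety.** The C1D8 bloods are the only scheduled on-treatment bloods that reflect monotherapy.
- **PK.** Duvelisib monotherapy PK is a secondary objective. The C1D8 samples taken before pembrolizumab are the only planned ones that follow repeated dosing without pembrolizumab. In Stage 2, the pre-pembrolizumab samples on C1D1 surround the first duvelisib dose.
- **Biomarkers.** The biopsy and immune-cell samples would reflect varying time on drug. These endpoints are exploratory (Table 5: "Required biopsies in Stage 1 and optional biopsy in Stage 2").

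A smaller matter arises on the late side. C1D15 has the only scheduled chemistry and hematology between C1D8 and C2D1, but it is tied to duvelisib Day 1. After a late pembrolizumab dose it can come sooner after that dose than planned.

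**Working it through.** **Inputs.** Table 1: C1D8 at D8 ± 5 and C1D15 at D15 ± 3. Sections 4.1 and 6.7: 1-week lead-in plus 3 weeks of combination. Section 6.1.1: duvelisib twice daily. Cycle 1 lasts 4 weeks, so nominal C2D1 is Day 29, with a ± 3 window.

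**Plan's own figure.** Lead-in = dose day - 1 = 8 - 1 = 7 days; 7 + 21 = 28 days. This agrees with the stated DLT period.

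**Permitted range.** 8 - 5 = Day 3 and 8 + 5 = Day 13, so 11 days are in-window. C1D15 runs from 15 - 3 = Day 12 to 15 + 3 = Day 18. Duvelisib doses before the visit = 2 × lead-in days, assuming two doses on every day including Day 1. C1D15 gap = visit day - pembrolizumab day.

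| First pembrolizumab dose | Lead-in (days) | Duvelisib doses before visit | C1D15 gap at nominal Day 15 | C1D15 gap, Days 12 to 18 |
|---|---|---|---|---|
| Day 3 | 2 | 4 | +12 | +9 to +15 |
| Day 7 | 6 | 12 | +8 | +5 to +11 |
| Day 8 | 7 | 14 | +7 | +4 to +10 |
| Day 13 | 12 | 24 | +2 | -1 to +5 |

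The -1 entry would need the visits to occur out of order and is not realistic.

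**Early side.** Days 3, 4, 5 and 6 give lead-ins of 2, 3, 4 and 5 days. These are 4 of the 11 permitted days, which counts what the window allows and does not estimate how often it would happen. With D8 -1/+5, the window is Days 7 to 13 and the lead-in 7 - 1 = 6 to 13 - 1 = 12 days.

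**Late side.** After a Day 13 dose, the nominal C1D15 visit is 15 - 13 = +2 days and the latest in-window visit 18 - 13 = +5. The next scheduled bloods are at C2D1, from 26 - 13 = +13 to 32 - 13 = +19 days. Timing the visit at 7 ± 3 days after the dose would give 13 + 7 ± 3 = Days 17 to 23. For a Day 8 dose the same rule gives Days 12 to 18, as now.

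**DLT period.** With a Day 3 dose, the third combination week ends on Day 3 + 20 = Day 23, inside the 28 days. No combination observation is lost.

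**The case against.** **A window is a tolerance, and the text directs Day 8.** Section 4.1 plainly describes a 1-week lead-in, and footnote i, attached to the pembrolizumab dose itself, contemplates only delay. A Day 3 dose would mean a site had set that direction aside. This makes very early dosing unlikely. It does not make it out of window: the only firm lower limit is the 2 days that the window implies.

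**The PK analysis can absorb it.** Section 9.4.6 plans population PK modelling, and Section 8.5 requires sample and dose times to be recorded, so a short lead-in would be visible and could be modelled. That stands as mitigation. A reader might infer either that the PK result is compromised or that it is safe. The documents support neither, because they give no half-life or time to steady state.

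**The late side is largely covered already.** A reader might infer that late dosing forces the mid-cycle bloods to about two days after pembrolizumab, too early to be useful. The documents do not support that. After a Day 13 dose, Days 17 and 18 are already in-window and give +4 and +5 days, and the plan itself accepts +4 for an on-time dose. No onset time for combination toxicity is given, and Stage 2 schedules no bloods between C1D1 and C2D1. Continuous safety monitoring, discretionary tests (Section 10.3), required contact with the Medical Monitor and the shifted DLT evaluation also help. This objection stands, so the late side is only a refinement.

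**Conclusion.** The point holds on the early side and is minor. Table 1 permits a 2-day lead-in where Sections 2.4.1, 4.1, 4.2 and 6.7 describe one week, and no rule addresses early dosing. The potential loss is shorter monotherapy safety observation, less time on drug before the exploratory biopsy and immune-cell samples, and possibly a C1D8 PK sample that is not at steady state.

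It is limited to about 13 Stage 1 subjects. A reader might suspect that it weakens the main decisions, but it does not touch the ORR test or the rule of at most 1 DLT in 6, and an early dose adds combination time to the DLT period.

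The conclusion assumes that the ± 5 heading is as intended (it repeats on each page of Table 1) and that Cycle 1 days count from the first duvelisib dose. How often sites would dose early is unknown.

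**What to change.** **Main change.** In Table 1, replace D8 ± 5 with D8 -1/+5 (Days 7 to 13). The late side can stay, since delay rules already exist. No visit or sample is added. The cost is less freedom to schedule the visit early.

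**Optional.** After a late first pembrolizumab dose, schedule the C1D15 visit at 7 ± 3 days after the actual dose, and change the Day 15 entry in both Table 1 and Table 2. The predose PK sample, vital signs and ECOG assessment at that visit would move with it. For a Day 13 dose the visit could fall on Day 23, three days before the earliest in-window C2D1 (Day 26).

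Either change needs an amendment with IRB/IEC approval (Section 10.6.1) and does not justify one alone. The June 2020 memorandum already holds a Stage 1 schedule correction, the Cycle 5 Day 1 PK draw, for any future amendment; these changes can go with it.
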